Data collection: daily PA measures, demographic details, co-morbidity status, physical frailty assessment, functional status, quality of life (QOL) and NEHA data

Consent: for participation in the study, physical frailty assessment, additional collection of retrospective CIED data, and access to electronic patient records

Data sources: CIED downloads, self-report questionnaire, physical measurements (height, weight, hand grip strength, gait speed), electronic hospital records, HES (hospital episode statistics) data

Results analysis: data will be analysed to investigate: daily PA variability; the association between PA and NEHAs, and the impact of frailty on PA patterns

Scientific and medical opportunities

This study will collect a unique set of new data for analysis. Combining expertise in Geriatric Medicine and Cardiology, this work will aim to provide a scientific basis for some of the fundamental assumptions made regarding health behaviours in later life. Little is known about normal day-to-day fluctuations in PA in an older population. This objective data will shed light on these patterns, and the temporal relationship between PA and NEHAs. Not only will this enhance our clinical knowledge, but it will provide the opportunity to develop proactive monitoring systems – potentially using PA as a proxy marker of health in certain older patient groups.

Expected outcomes

This study expects to find that NEHAs are commonly preceded by a demonstrable acute decline in PA. Various models will be tested to demonstrate predictive validity. This association is expected to vary by patient sub-groups defined by baseline health status (co-morbidity burden, degree of frailty), and demonstrated underlying activity pattern.

Further avenues for research

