By the nature of this study, participants are limited to those with a compatible CIED i.e. have some form of cardiac disease (the majority HF and/or conduction disorders). Cardiovascular disease is a fundamental pillar of ageing, lying on the spectrum of physiological frailty – inherent, and relevant to all older people (43). Therefore, on balance we do believe this population sample is generalisable to an older population with comparable functional status and degree of frailty. This study will be looking at temporal pattern analysis, using this population as a cohort of older people with a common age-associated long-term condition (heart disease). There is no reason to expect this group of patients would behave any differently with regard to PA and major health events compared with any other older patient group. Therefore we believe these results will be of interest out with the cardiac community.

Sample Size Calculations

Using data from previous analyses (21, 22) sample size calculations have been performed based on the Kesley and Fleiss formulas for 'cohort studies', using exposure = low/decline in PA and outcome = NEHA within 6 weeks. We considered a relative risk (RR) of 2.5-3 to be clinically significant in terms of a PA trigger signifying increased risk of NEHA. Sample size estimate thus = **150** participants (using inputs: 95% significance, 80% power, RR 2.5-3, output: 88 – 198, see *Table 1*).

Table 1: Sample size calculations

Variables	Option 1	Option 2	Option 3	Option 4
Two-sided significance level (1-alpha)	95	95	95	95
Power (1-beta, % chance of detecting):	80	80	90	90
Percent of Unexposed with Outcome:	17	17	17	17
Percent of Exposed with Outcome:	43	51	43	51
RR	2.5	3	2.5	3
Ratio of sample size, unexposed/exposed:	4.4	4.4	4.4	4.4
Sample size: Kesley	133	81	177	108
Sample size: Fleiss	145	88	198	121

The SENSE HF study (enrolling adult patients with chronic, stable HF, 6 months follow-up) captured 224 'unscheduled hospital visits' in 132 patients over 659 patient years, i.e. an annual rate of 34%. (44) Using this as a guide, with a sample size of 150 (150 patient years) we would expect to capture approximately 51 NEHA episodes from retrospective data collection.

Study Objectives

1. Describe the relationship between PA and NEHAs in an older CIED cohort
2. Describe daily variability of PA in an older CIED cohort
3. Describe the relationship between PA and NEHAs, and examining whether frailty moderates this relationship

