4. Confirm/refute the clinical observation that a drop in PA tends to precede episodes of NEHA in later life, and if so, evaluate predictive value

Study Design

Type

Observational study

Setting

Manchester University NHS Foundation Trust (MFT). This includes the trust's 2 main sites: Manchester Royal Infirmary and Wythenshawe Hospital.

Duration of Study

18 months

Participants

Inclusion/exclusion criteria are shown below, with reference to *Table 2* that lists compatible CIEDs for this study.

Inclusion Criteria

1. Age 60+ years
2. Functioning CIED in situ for at least 6 months
3. Medtronic manufactured device compatible with CareLink® Cardiac Compass application (platform which measures and stores physiological parameters)
4. Lives in the Greater Manchester area
5. Able and willing to give written, informed consent to enter the study

Exclusion Criteria

1. Faulty or incompatible device
2. Immobile (unable to walk in upright position)
3. Active participant in a clinical trial which does not allow concurrent recruitment into this study
4. People unable to consent in the English language (including the understanding of study literature which is published in English only)

Patients may be entered into registries, observational studies or clinical trials while also participating in PATTern.

Justification of Study Design

Study design

Research question: what are the normal variations in daily PA in later life, and how does PA change surrounding major health events?

This question is best answered by an observational study, as we are attempting to establish normal patterns of behaviour. Measuring PA using sensor devices allows for the passive collection of objective data. The use of retrospective PA data from CIED devices minimises participation bias (i.e. inadvertently influencing behaviour). Using a cohort of older people with CIEDs limits analysis to a particular cohort of older people, however as explained below in the 'generalizability of results' section, this analysis will still be of great value, and on the whole generalizable to the broader population. Specific considerations related to the PATTErn study are discussed in more detail below.

Selection Bias

Selection bias will be introduced by our inclusion/exclusion criteria and recruitment method in the following ways:

1. Inclusion criteria
 - 1.1. compatible CIED in situ
 - 1.1.1.The most frail patients would not be eligible/suitable for CIED implantation

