[figure not shown]

Figure 2: Screening and recruitment flowchart

The CtC form (see supporting documents) will include a phone number for the research team, as well as a slip form for the patient to send back to the research office (a freepost envelope will be

provided). All patients whom indicate they have consented to be contact (either by directly contacting research team or by returning a slip form) will be noted in the screening log (“screening⁺, CtC⁺”). The researcher will contact the patient in their preferred method of communication (phone, email, letter) and send out a patient information sheet (PIS). The patient will then be re-contacted (in their preferred method of communication) to establish if they are willing to come in 20-30minutes prior to their scheduled annual device follow-up appointment to speak to the researcher. A further list of “screening⁺, CtC⁺, engagement⁺” patients will be documented in the screening log. A reminder contact will be made 1-2 weeks prior to their scheduled appointment.

The researcher will meet all “screening⁺, CtC⁺, engagement⁺” patients 20-30 minutes prior to their scheduled appointment to allow time to obtain written, informed consent. After a patient has consented to participate, they will be allocated a unique randomly generated study participant number (SPN). A list of consented patients with corresponding study numbers will be kept in the enrolment log in the site file. All study data there in will be identified using this SPN.

18 months has been allocated for recruitment. It is anticipated all recruitment will be undertaken by the PI. Recruitment will not cease once 150 participants have been recruited; rather cease at the end of this 18-month window. This will maximise impact of results and reduce risk to the study if number of captured NEHAs is less than expected.

Rationale for screening and recruitment strategy

Recruitment at annual device follow-up clinic

In order to minimise burden of participation for patients and reduce the cost of the study, we have chosen to recruit patients whilst they attend hospital for pre-scheduled clinic. It is not anticipated this will cause any significant delays/inconvenience for the normal running of the clinic.

Screening by care team

Although the PI is a member of the care team and research team, we have separated out these roles to make it clear how data will be handled.

Consent to contact

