For this study, major health events are defined as NEHA episodes. Daily PA in the days leading up to NEHA episodes will be compared to a participant's MDPA, in order to define across the cohort when any observable change in PA is detected by this method. To explore trends in PA preceding NEHA episodes, a nested case control study will be constructed within the dataset, comparing trends in PA preceding NEHA episodes with general trends in PA before index times with no NEHA episodes. This will allow the creation of various 'PA markers' for diagnostic test evaluation methods (sensitivity/specificity, positive and negative predictive value). These PA markers will then be investigated to ascertain if they predict PA subtypes i.e. long-term behaviour patterns. We will also look at how these 'markers' superimposed on identified subtypes can be used to potentially personalise alert systems.

In a similar fashion, we will also explore PA trends following NEHA episodes. There is very little published data on 'recovery time' following hospitalisation episodes in an older population. This study is not powered to investigate this as a primary outcome, however we will measure 'time till PA recovery' following NEHA subtypes (A&E attendance and non-elective hospitalisation episodes), and examine determinants of this.

Risks to Study

Recruitment

A snapshot 'screening' audit using Cardex data in October 2016 found 341 potentially eligible patients on CIED annual follow-up at Manchester Royal Infirmary, an additional 150-250 patients at Wythenshawe are anticipated to be eligible. Recruitment will be undertaken by the PI. An 18-month period has been allocated for initial recruitment. Based on observational studies in similar population, we anticipate a take-up rate of from screening of between 60-80% (56).

Efforts made to maximise recruitment:

- Rigorous screening process
- Recruitment from existing clinical visits
- Low burden of assessment

In the event of lower than anticipated take-up, the recruitment window could be extended beyond 18 months to reach required sample size.

Missing data

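### The plan does not say in which data PPV and NPV of the PA markers are calculated; taken unweighted from the nested case-control sample, they would rest on an event fraction set by the number of controls

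*Combined protocol and SAP*

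**What the plan says.** Objective 4 asks whether a fall in PA precedes NEHA episodes, "and if so, evaluate predictive value". The Expected outcomes part of the Summary adds: "Various models will be tested to demonstrate predictive validity".

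The method is in Statistical Analysis, under PA and major health events. A case-control study is nested in the dataset, "comparing trends in PA preceding NEHA episodes with general trends in PA before index times with no NEHA episodes". The next sentence reads: "This will allow the creation of various 'PA markers' for diagnostic test evaluation methods (sensitivity/specificity, positive and negative predictive value". The same paragraph then considers using the markers to personalise alert systems.

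That section does not say:
- in which data PPV and NPV are calculated;
- how many control index times are taken per case, or how they are sampled;
- whether controls are weighted back to the cohort;
- over what period ahead a marker is meant to predict;
- how accuracy is validated internally.

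No other section supplies these. The multilevel models under PA patterns use activity subtypes, not these markers, as exposures. Sample Size Calculations does define a horizon, "using exposure = low/decline in PA and outcome = NEHA within 6 weeks", but it is not carried into the marker evaluation.

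**The concern.** In a case-control sample the analyst chooses how many non-events accompany each event. Sensitivity and specificity condition on outcome status, so they survive this if controls are a random draw of non-event times. PPV and NPV condition on the marker, so they need the event fraction of the population in which the marker would be used. If they are read from the sample without weights, that fraction is a design choice. The resulting PPV is then not the chance that a patient who shows the marker will attend hospital.

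Predictive value is a named objective, and the Summary says the results will guide local pilot studies. For an alert, PPV is a central quantity. The distortion can go either way, and the plan does not let a reader tell which.

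**Working it through.** **Inputs.** Table 1, Options 1-2: outcome in 17% of unexposed and 43% or 51% of exposed, with 4.4 unexposed per exposed. Heart failure study cited in Sample Size Calculations: "captured 224 'unscheduled hospital visits' in 132 patients over 659 patient years". Control ratios of 1:1, 1:4 and 1:9 are my assumption, because the plan gives none.

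**The plan's own figures.** It states no PPV or NPV. Its event count reproduces: 150 × 224/659 = 51.0, against "we would expect to capture approximately 51 NEHA episodes from retrospective data collection". Table 1 also reproduces to within one participant: Kelsey 132/81/177/108 against 133/81/177/108 stated, and Fleiss 144/88/198/121 against 145/88/198/121. So the inputs are read as the authors used them.

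**Accuracy implied by Table 1.** The exposed share is 1/5.4.
- Option 1: risk p = (4.4 × 0.17 + 0.43)/5.4 = 21.8%; sensitivity = (0.43/5.4)/0.218 = 36.5%; specificity = (0.83 × 4.4/5.4)/0.782 = 86.5%.
- Option 2: p = (4.4 × 0.17 + 0.51)/5.4 = 23.3%; sensitivity 40.5%; specificity 88.2%.

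**Predictive values.** PPV = Se·p/[Se·p + (1−Sp)(1−p)] and NPV = Sp(1−p)/[Sp(1−p) + (1−Se)p]. In an unweighted sample with m controls per case, p is replaced by 1/(1+m).

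| Event fraction | PPV, Option 1 / 2 | NPV, Option 1 / 2 |
|---|---|---|
| 1:1 (50%) | 73.0 / 77.4% | 57.7 / 59.7% |
| 1:4 (20%) | 40.3 / 46.1% | 84.5 / 85.6% |
| 1:9 (10%) | 23.1 / 27.6% | 92.5 / 93.0% |
| Cohort at Table 1 risk | 43.0 / 51.0% | 83.0 / 83.0% |

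Sample and cohort values agree only when m = (1−p)/p, which is 3.6 (Option 1) or 3.3 (Option 2).

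**Weighting check.** Multiplying controls by [(1−p)/p]/m returns 43%/83% and 51%/83% at 1:1, 1:2 and 1:4, so weighting removes the dependence on m.

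**A lower event risk.** The cited study's 659 patient-years contain 659 × 365/42 = 5,727 six-week windows. With 224 visits in 132 patients, between 132 and 224 windows hold an event: 132/5,727 = 2.3% to 224/5,727 = 3.9%. Now keep the plan's relative risk (RR) of 2.5-3 and its 4.4 ratio. The unexposed risk is p0 = 5.4p/(4.4 + RR) and the cohort PPV is RR × p0.
- Lowest: RR 2.5, p = 2.3%: p0 = 1.80%, PPV = 4.5%.
- Highest: RR 3, p = 3.9%: p0 = 2.85%, PPV = 8.6%.

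For that marker, sensitivity is RR/(4.4 + RR) = 36.2% or 40.5%. Specificity is (4.4/5.4)(1−p0)/(1−p), about 82%. Unweighted PPV would read 67-70% at 1:1, 33-37% at 1:4 and 18-20% at 1:9. All three lie well above 4.5-8.6%.

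**The case against.** The strongest reply is that the plan never says PPV and NPV will be calculated in the sampled set. Literally, the case-control study allows markers to be created; they could then be scored elsewhere. The text does not even say that only a subset of event-free time will be drawn. Daily PA and 12 months of hospital records are collected for each participant, so cohort-wide scoring is feasible. This stands: the harm depends on a reading. But the text goes straight from the case-control contrast to the four accuracy measures, and no other section mentions cohort scoring or weights.

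It is also fair that the error can be small. At Table 1's risk, four controls per case gives a PPV of 40-46% against 43-51%. The low-risk case borrows a rate from adults with stable heart failure, whereas this study counts all-cause attendances in people aged 60 or over with any compatible device. The work is exploratory, its use in alerts is only a possibility, and no sample size rests on PPV.

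Three stronger inferences are not supported:
- A reader might infer a conflict between the activity measurements at day −1 to day −14 and the six-week horizon. The former look back from an event and the latter is an outcome period, so they are compatible; what is missing is a stated window for the markers.
- A reader might carry Table 1's sensitivity and specificity down to 2.3-3.9% and obtain a PPV of 6-12%. That breaks the plan's own RR and 4.4 ratio; keeping those gives 4.5-8.6%.
- A reader might infer that small numbers make the accuracy figures badly optimistic. The plan does not define the candidate markers or cut-points, and "Recruitment will not cease once 150 participants have been recruited", so the size of any optimism cannot be fixed from the documents.

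**Conclusion.** The point holds as a conditional one and should be fixed. The plan links a case-control sample to PPV and NPV without weighting or cohort-wide scoring. On the most direct reading, the event fraction behind both would be set by the number of controls, not by patients' risk.

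The documents do not show that an unweighted PPV is planned. Nor would PPV and NPV become unrelated to the marker: they would still depend on its sensitivity and specificity, which are sound if controls are randomly drawn from non-event times.

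On size, one marker could be reported with a PPV anywhere from 23% to 77% across the ratios tried, against 43-51% at Table 1's risk. NPV could read 58% to 93%, against 83%. If the six-week risk were 2.3-3.9%, the cohort PPV would be about 4.5-8.6% and the gap larger. These figures rest on assumed control ratios, on the sample-size exposure standing in for a PA marker and, for the last range, on transferring the heart failure study's rate to this cohort.

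**What to change.** In Statistical Analysis, under PA and major health events:

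1. Keep the case-control contrast for describing trends, and state how control index times are sampled and how many are taken per case.
2. State the prediction window for the markers.
3. Compute PPV and NPV by applying each marker to all eligible person-time of all enrolled participants over that window. Alternatively, weight controls by the inverse of their sampling fraction.
4. Because no separate data are named for evaluating the markers, report accuracy after cross-validation or bootstrap optimism correction, keeping each participant's windows together.

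The cost is a few sentences and a little more analysis work; no new data are needed. The downside is that the accuracy figures may look less favourable.

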Stroke/TIA	
 • Self-report • Coded on electronic medical records

	
• Brain imaging demonstrating previous ischaemic or haemorrhagic event
--	--

Withdrawal from Study

All participant derived data will be collected on the day of consent, bar the occasional case where a participant wishes to take the questionnaire home and post in back at a later date. Given the short period of time each participant will be actively enrolled in the study, it is highly unlikely a withdrawal of consent will occur. In the event of withdrawal of consent, a consent withdrawal form will be used to document this event. All data collected up to the date of consent withdrawal will be retained, but no further outstanding data collected. This will be made clear in the study information and consent form.

Statistical Analysis

Basic variables from CIED data

CIED data will be processed to create a new set of basic variables for analysis.

1. Mean daily physical activity (MDPA) – mean PA across dataset
2. PA intra-individual variability – as measured by:
 - Range
 - Interquartile range
 - Mean absolute deviation
3. PA surrounding NEHAs – multiple measures.

DOEDA = date of emergency department attendance; DOA = date of hospital admission; DOD = date of discharge; LOS = length of stay (DOD-DOA)

- Difference in PA from MDPA on DOEDA/DOA day -1, day -2, day-3, day-7, day -14
- Difference in PA from MDPA on DOEDA/DOD day +1, day +2, day+3, day+7, day +14
- ‘Time till PA recovery’ – time from DOEDA/DOD to day regained \geq MDPA

Descriptive analyses

All data will be stored and analysed using SPSS and ‘R’ statistical computing software. Basic descriptive statistics will be used to compare different sub-groups of participant (e.g. frail v non-frail). MDPA will be used to facilitate basic comparative analysis using a continuous variable. Determinants of MDPA will be calculated using univariate and multivariable analysis.

PA patterns

As demonstrated in *Figure 3* below, common activity patterns embedded within CIED PA data will be identified using clustering algorithms. Using these identified subtypes of PA as exposures in a longitudinal model with outcome NEHA, multilevel/hierarchical modelling methods (both classical and Bayesian approaches) will be utilised to investigate associations with outcome.

[figure not shown]

Figure 3

PA and major health events

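### No step separates deriving the PA markers from testing their accuracy, so any marker or cut-off chosen on these data will on average look more accurate than it is

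*Combined protocol and SAP*

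**What the plan says.** Objective 4 asks whether a fall in PA tends to come before a NEHA and, "if so, evaluate predictive value". The Summary (Expected outcomes) adds: "Various models will be tested to demonstrate predictive validity".

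The analysis is in Statistical Analysis, PA and major health events. PA before NEHAs is compared with each participant's own mean (MDPA) "in order to define across the cohort when any observable change in PA is detected by this method". Then "a nested case control study will be constructed within the dataset", which sets PA before NEHAs against PA before index times without one. The markers come out of that comparison and are intended for "diagnostic test evaluation methods (sensitivity/specificity, positive and negative predictive value".

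The candidate measures are under Basic variables from CIED data: "Difference in PA from MDPA on DOEDA/DOA day -1, day -2, day-3, day-7, day -14". That is five lags, with no cut-off attached to any of them.

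Sample Size Calculations gives the expected yield: "we would expect to capture approximately 51 NEHA episodes from retrospective data collection".

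**The concern.** A marker's sensitivity and specificity are unbiased when the marker and its cut-off were settled without looking at the outcomes they are scored on. Here the markers do not exist until NEHA and non-NEHA times have been compared, and the only data described for scoring them are those same data. Choosing a lag, a cut-off or a model because it separates these episodes well, and then reporting how well it separates them, credits the marker with chance features of the sample. This happens even when the drop in PA is real. It is a different matter from the false-positive rate of testing several days, and from how the control times are sampled.

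Objective 4 rests on these accuracy figures. The Summary says that the results will guide local pilots of clinical summaries, and the analysis section links the markers to personalised alerts. The Background reports that the predictive accuracy of PA on its own has so far been poor, so an excess of the size shown below could be mistaken for an advance.

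**Working it through.** **1. What the plan provides to separate derivation from testing**
- Marker and cut-off fixed in advance: none. The device rule in CIED remote monitoring (fewer than 60 active minutes in a week) is described as background and is not adopted as a study marker.
- Hold-out set, cross-validation, bootstrap or external sample: none described.
- The two HES requests (6 and 18 months) are not assigned as development and test sets, and the Data Management Plan describes one combined analysis database.

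**2. Number of episodes**
- Plan's figure: 150 × 224/659 = 51.0. It reproduces.
- Lower scenario: if the cited trial's ratio of 132 patients to 659 patient-years carried over, the episodes would come from 150 × 132/659 = 30 patients. Treating each patient as one independent case gives 30.
- Upper scenario, from Risks to Study (Recruitment): (341 + 150) × 0.60 = 295 to (341 + 250) × 0.80 = 473 participants. At 34% per year this gives 100 to 161 episodes.

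**3. Size of the excess**

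Youden index J = sensitivity + specificity − 1. For a normal marker with SD 1, shifted by d before a NEHA, a cut-off c has true sensitivity 1 − Φ(c − d) and true specificity Φ(c). In each simulated dataset the marker and cut-off with the largest observed J are chosen. Excess = observed J − true J of that same rule.

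Assumptions that are not in the documents: normal markers, independent cases, four control times per case, and selection by maximum J. For five lags the correlation between days is r to the power of the lag difference, with r = 0.4 (weak) or 0.9 (strong). There were 2,000 datasets per cell. The three entries in each cell are for true drops of 0, 0.3 and 0.5 SD.

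| Cases | One marker, cut-off searched | Best of five, r = 0.9 | Best of five, r = 0.4 |
|---|---|---|---|
| 30 | 0.119, 0.112, 0.107 | 0.176, 0.171, 0.166 | 0.199, 0.195, 0.191 |
| 51 | 0.093, 0.083, 0.077 | 0.138, 0.134, 0.129 | 0.155, 0.149, 0.148 |
| 100 | 0.067, 0.059, 0.053 | 0.100, 0.094, 0.090 | 0.111, 0.106, 0.101 |
| 161 | 0.053, 0.044, 0.039 | 0.080, 0.073, 0.071 | 0.087, 0.084, 0.081 |

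One cell in full (51 cases, best of five, r = 0.4, drop 0.5 SD): sensitivity 0.686 observed against 0.566 true; specificity 0.649 against 0.621; J 0.335 against 0.187. Excess = 0.335 − 0.187 = 0.148.

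A second set of runs used equally correlated markers, true AUC 0.5 to 0.8, 30 or 51 cases, and control ratios of 1:1 and 1:4. J was too high in every scenario, by 0.06 to 0.18. With 20 controls per case and five markers the excess was still 0.13 to 0.14.

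**4. What removes it**
- One marker with a cut-off fixed in advance (AUC 0.70, 51 cases): mean observed sensitivity 0.644 against 0.645 true, so no bias. Precision is still limited: 36 of 51 detected has an exact 95% interval of 0.56 to 0.83.
- Bootstrap correction (51 cases, 204 controls, five markers correlated 0.5). At AUC 0.70, J goes from 0.404 to 0.318 with truth 0.278, removing (0.404 − 0.318)/(0.404 − 0.278) = 68% of the excess. With useless markers, J goes from 0.141 to 0.049 with truth 0, removing 0.092/0.141 = 65%. The correction is substantial but partial.

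**The case against.** The strongest reply is that the plan never says it will search for cut-offs, pick a best marker, or score markers on the episodes that produced them. It speaks of several markers, and reporting every one of them is a natural reading; the gain from picking the best of five would then not arise. The section is also partly exploratory in tone, and pilot testing is placed after this study.

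Much of this stands. A reader might infer that the plan prescribes selecting and testing on the same episodes. It does not: that is what happens by default if nothing is added. Reporting all markers removes the selection among lags but not the cut-off problem. Sensitivity and specificity need a cut-off, none is given, and a cut-off searched for a single marker still inflates J by about 0.08 to 0.09 at 51 episodes. An exploratory label does not help either, because the Summary speaks of demonstrating predictive validity.

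The size also depends on the setting. A reader might take 0.15 as a general figure. It belongs to 51 episodes and five weakly correlated lags. Recruitment is planned to continue past 150 within the 18-month window, and more episodes would shrink the excess; clustering of episodes within patients would enlarge it.

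Finally, a reader might conclude that a marker is bound to look useful and then fail in the pilots. The documents do not support that. The bias is an average, and with a small true effect even the inflated J is modest.

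**Conclusion.** The point holds as a missing safeguard. Followed as written, the plan yields apparent accuracy for objective 4, and on average that is too high if the marker or the cut-off is chosen on the study data. The direction follows from the selection itself; the size rests on the assumptions listed in the working.

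At the plan's 51 episodes the excess in J is about 0.08 to 0.09 with one marker and a searched cut-off, and about 0.13 to 0.15 with the best of five lags. Over 30 to 161 cases it is about 0.04 to 0.20. There would be no such bias if one marker and cut-off were fixed before the NEHA data were seen, but the plan does not say this will be done. The sample size and the expected episode count are unaffected.

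**What to change.** In Statistical Analysis, PA and major health events, adopt one of the following.

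(a) Name one primary marker, for example a stated lag of the difference from MDPA already listed under Basic variables, and fix its cut-off before the NEHA data are linked. This removes the bias for that marker.

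(b) If markers and cut-offs are to be derived from the data, repeat the whole selection of marker, cut-off and any model inside a bootstrap or cross-validation that resamples participants rather than episodes. Report the corrected sensitivity, specificity and predictive values beside the apparent ones, and label them development-stage because the correction is partial.

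Under either option the device's weekly low-activity rule may be shown as a secondary comparator that needs no cut-off search. State that it measures low activity in absolute terms, whereas objective 4 concerns a drop from the participant's own level.

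The cost is some extra analysis code and less favourable stated accuracy. No new data or change in recruitment is needed.
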